7.10 Unscheduled Visit

An unscheduled visit following a participant's request or the site investigator's recommendation should be recorded on the appropriate CRF. The following procedures and assessments may be performed at the unscheduled visit:

1. Staff will review the memory aid with the participant. The participant will be asked about symptoms, concomitant medications and any medical problems since the last visit, which will be recorded on the appropriate CRF. Additionally, the participant will be asked to provide exact dates and times of the study product administration.
2. Medical, gynecological and sexual history to include assessment of STI and HIV risk
3. Symptom-directed physical and pelvic examination by a study physician or nurse that will include vital signs, including temperature, and examination of respiratory and cardiovascular systems, as well as assessment of symptoms and adverse events
4. The pelvic examination will be conducted in the following order:
 - a. Examination of the external genitalia
 - b. Speculum insertion and examination of vagina, fornices and cervix with naked eye. Water will be used to ease speculum insertion. No lubricant should be used as it could contain chlorhexidine which may kill *Lactobacillus*.
 - c. Vaginal pH
 - d. Vaginal swab for wet mount taken from the posterior fornix for yeast vaginitis and clue cells and for amine test (whiff test)
 - e. Vaginal swab for Gram stain (Nugent scoring system)
 - f. Vaginal swabs (no more than two) for storage and future identification of vaginal bacteria, and possible multiomic (e.g. proteomics, metabolomics, etc.) testing
 - g. Vaginal swabs for *L. crispatus* identification with qPCR
 - h. If indicated, cervical (or vaginal) swab for nucleic acid amplification of *N. gonorrhoeae*, *C. trachomatis*, and *T. vaginalis*
 - i. Other tests as deemed necessary by the site investigator in response to symptoms presented at this visit
5. If indicated, clean catch urine dipstick; urinalysis if abnormal results indicate
6. If indicated, β hCG pregnancy test
7. All clinical and laboratory findings at the time of the evaluation will be recorded on the CRF. These findings will include observations present on the pelvic exam such

- as genital findings including location; presence or absence, and character of vaginal or cervical discharge or lesions; and results of any on-site tests.

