3.3.2. Recurrent BV

By standard definition, a treatment of BV is only considered to have failed if Amsel criteria or Nugent score on Gram stain diagnose BV to persist at 22-30 days after the initiation of the antibiotic treatment. As a result, women who continue to have BV during the enrollment visit will not be re-treated with MetroGel at the time of enrollment, as additional time is needed for BV to resolve after antibiotic treatment. Thus, they are not considered treatment failures at this time (approximately 2 days after termination of antibiotic treatment). All BV diagnoses following enrollment are considered incident, as they occur at least 22-30 days after the commencement of MetroGel treatment and consequently are treatment failures or new infections. And so, a positive diagnosis of BV at any visit after the enrollment visit will be considered a recurrence of BV (i.e. there

is no distinction between treatment failure and new infection). A positive diagnosis of BV at the enrollment visit will not be considered a recurrence of BV.

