4.5. Efficacy and Safety Variables

For safety and efficacy analyses, multiple observations within specific visit period are accepted. In the case of multiple observations within a specific window, the assessment value that is closest to the scheduled visit window will be used in the analyses for the post-baseline records. The last observed value prior to administration of LACTIN-V or placebo will be used as the baseline value. All the recorded data will be listed. If observations have the same distance to the scheduled assessment, the latest one will be used.

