8. EFFICACY EVALUATION

8.1. Primary Efficacy Analysis

For the primary analysis, the cumulative proportion of BV recurrence by Visit 4 (Week 12) will be summarized by treatment group. A formal hypothesis test will be performed with null hypothesis that the cumulative proportion of BV recurrence by Visit 4 (Week 12) in the LACTIN-V group is equal to that in the placebo group and alternative hypothesis that they are not equal. Cumulative proportion of BV recurrence is defined as follows: the numerator is the number of subjects who experience recurrence at least once through Visit 4 in the particular analysis population and the denominator is the number of subjects included in the particular analysis population. [Table 11](#) will present the cumulative proportion of BV recurrence by Visit 4 (Week 12) (and 95% Wilson confidence interval) in each treatment group along with the odds ratio of BV recurrence proportions between treatment groups (and 95% asymptotic confidence interval). The p-value from the Chi-Square test will be presented. The summaries will be calculated in the ITT, mITT, CC, and PP populations, where the ITT and mITT summaries will be replicated using the imputation methods described in Section 6.5. [Listing 6](#) will present individual efficacy data for all subjects.

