As an additional analysis of the outcome measures of BV recurrence by Visit 4 and by Visit 7, the median time to BV recurrence (from randomization) will be estimated by treatment group using Kaplan-Meier estimates ([Table 17](#) and [Table 18](#)). In addition, the median 95% confidence interval, minimum, first quartile, third quartile, and maximum estimates of time to BV recurrence will be presented. For subjects who experience BV recurrence by Visit 4 (Week 12), the time of BV recurrence will be defined as the midpoint between the earliest time point of a positive BV diagnosis (post-baseline) and the previous observed time point. For subjects without BV recurrence at or before Visit 4, the BV recurrence endpoint will be coded as censored, with time to recurrence defined as the elapsed time from the first dose of study product, to the Visit 4 time point, or to the first occurrence of loss to follow-up or the time-point at which the subject became ineligible for the particular analysis population. Time to BV recurrence by Visit 7 (Week 24) will be defined similarly. The analyses will be performed in the ITT, mITT, CC, and PP populations, where the ITT and mITT summaries will be replicated using the imputation methods described in Section 6.5. Kaplan-Meier curves for BV recurrence will also be generated for each analysis population by Visit 4 (Week 12) and by Visit 7 (Week 24), respectively ([Figure 2](#) and [Figure 3](#)).

As a sensitivity analysis of the outcome measures of BV recurrence by Visit 4 and by Visit 7, the cumulative proportion of BV recurrence analyses will be repeated in the mITT and CC populations after removing the subjects who received additional treatment for BV as documented in the concomitant medications CRF after the beginning of administration of LACTIN-V or placebo and before Visit 4 and before Visit 7, respectively (Table 19 and Table 20).

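### SAP 4.5's one-value-per-window rule, read literally, can drop a positive BV result that SAP 3.3.2, 8.1 and 8.2 count as recurrence, and 3.3.2's 22-day premise fails for very early unscheduled visits

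*SAP*

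**What the plan says.** **The general rule.** The opening text of SAP 4.5 (Efficacy and Safety Variables) covers both kinds of analysis and makes no exception. Within a window, "the assessment value that is closest to the scheduled visit window will be used in the analyses for the post-baseline records". For ties: "If observations have the same distance to the scheduled assessment, the latest one will be used".

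**The endpoint definition.** SAP 3.3.2: "a positive diagnosis of BV at any visit after the enrollment visit will be considered a recurrence of BV". SAP 8.1 builds the primary proportion on this: "the numerator is the number of subjects who experience recurrence at least once through Visit 4 in the particular analysis population". SAP 8.2 dates the event for the Kaplan-Meier analysis at "the midpoint between the earliest time point of a positive BV diagnosis (post-baseline) and the previous observed time point".

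**The premise.** SAP 3.3.2 justifies counting every positive after enrollment "as they occur at least 22-30 days after the commencement of MetroGel treatment". The same paragraph says that BV still present shortly after treatment is not yet a failure.

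**Where extra results come from.** Protocol 7.10: "An unscheduled visit following a participant's request or the site investigator's recommendation should be recorded on the appropriate CRF". No earliest day is set. The procedures that may be done there include pH, wet mount with whiff test, and "Vaginal swab for Gram stain (Nugent scoring system)". The schedule of events (Protocol Appendix A, SAP Table 2) marks these tests for unscheduled, product-discontinuation and early-termination visits as well.

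**The concern.** A cumulative endpoint of the type ever positive through Week 12 has to use every evaluable result. A rule that keeps one value per window suits a by-visit table but works against such an endpoint, because it can discard the only positive a woman has. As written, a programmer who follows 4.5 and one who follows 3.3.2 and 8.1 can code the primary outcome differently for the same woman, with both able to cite the SAP.

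The 22-day premise raises a different question. The rule in 3.3.2 is clear: any positive counts. Its stated reason does not cover visits held before failure can be judged on the SAP's own terms. A woman whose BV has not yet cleared, seen early because of symptoms, would be a recurrence permanently, even if she is clear at every later visit.

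**Working it through.** **1. The plan's own figure.** Inputs from SAP 5: 30% v 15%, 2:1 allocation, 5% level (two-sided per SAP 6.1), 70% power, Pearson chi-square, 10% drop-out. The usual formula with pooled variance under the null and no continuity correction gives 68 placebo + 136 LACTIN-V = 204. Inflating, 68/0.9 rounds up to 76, and 76 x 3 = 228. The stated size reproduces. With 228 x 0.9 = 205.2 complete cases (68.4 and 136.8), power is 70.4%, and expected events are 68.4 x 0.30 = 20.5 and 136.8 x 0.15 = 20.5, about 41 in all. The sample size is not in question.

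**2. The two rules on the same data.** The Visit 4 window is Days 77-91, target Day 84 (Protocol 7.5). Take a woman with no other positive and no BV treatment.

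| Results | SAP 4.5 keeps | Status under 4.5 | Status under 3.3.2 and 8.1 |
|---|---|---|---|
| Positive Day 80, negative Day 84 | Day 84 (distance 0 v 4) | Not recurrent | Recurrent |
| Positive Day 80, negative Day 88 | Day 88 (tie at 4, latest taken) | Not recurrent | Recurrent |

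If closeness is measured to the window rather than to the target day, all in-window results are at distance zero, the tie rule applies, and the later negative again wins.

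**3. What limits this.**
- Only results sharing a window compete. The windows for Visits 2-4 (Days 21-35, 49-63, 77-91) cover 45 of the 90 days from Day 2 to Day 91.
- A positive kept at any other visit restores the recurrence.
- SAP 6.3.2 counts as recurrent a woman who starts other BV treatment, or who stops product or withdraws for lack of effect. It does not say whether repeat study MetroGel is other treatment. Protocol 7.10 does not retreat asymptomatic BV, so those positives have no such backstop.
- The case review committee (SAP 6.3.2.5) is blinded to BV outcome, so it cannot restore a dropped positive.

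**4. The 22-day premise.** The fifth MetroGel dose falls 4 days after the first (5-day course) or at most 6 days after it (7 days with make-up doses, SAP 4.4.3). Enrollment, study Day 1, follows 12-48 hours later, that is 0.5-2 days. Study day on which 22 days is reached = 1 + 22 - (days from first dose to Day 1).

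| Course | Gap | First dose to Day 1 | 22 days reached on study day | Day 21 is, after start |
|---|---|---|---|---|
| 5 days | 12 h | 4.5 | 18.5 | 24.5 days |
| 5 days | 48 h | 6.0 | 17.0 | 26.0 days |
| 7 days | 12 h | 6.5 | 16.5 | 26.5 days |
| 7 days | 48 h | 8.0 | 15.0 | 28.0 days |

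The earliest in-window Visit 2 (Day 21) is at least 24.5 days after start, so scheduled visits meet the premise. An unscheduled positive on Day 10 is 9 + 4.5 = 13.5 to 9 + 8 = 17 days after start, and still counts.

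**5. Sensitivity, on assumed rates.** The documents give no frequency for either case. The rates below are assumptions, equal in both arms, applied to the 205.2 complete cases.

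*Dropped positives:* a fraction f of recurrent women lose their only positive, so the proportions become 0.30(1 - f) and 0.15(1 - f).

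| f | Events lost per arm | Power |
|---|---|---|
| 0 | 0 | 70.4% |
| 2% | 0.4 | 69.3% |
| 5% | 1.0 | 67.7% |
| 10% | 2.1 | 65.0% |

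*Early positives counted:* a fraction e of otherwise non-recurrent women are counted, so the proportions become 0.30 + 0.70e and 0.15 + 0.85e.

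| e | Relative reduction | Power |
|---|---|---|
| 0 | 50.0% | 70.4% |
| 1% | 48.4% | 68.4% |
| 2% | 46.8% | 66.5% |
| 5% | 42.5% | 61.0% |

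Imbalance matters more than the total. At design counts of 20/68 v 21/137 the Pearson test gives p = 0.018. Removing two positives from each arm gives 0.027; removing two from placebo alone gives 0.056. Nothing in the documents suggests such an imbalance.

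**The case against.** The best defence is that the specific definition governs. SAP 4.5.2, inside the same section, sends the reader to 3.3 for efficacy definitions and names BV recurrence as the primary variable. Sections 3.3.2, 8.1 and 8.2 all point to any positive, and none applies the closest-value rule to the cumulative endpoint. The SAP also treats 4.5 as a default elsewhere: its last-value-before-dosing baseline is replaced for BV by the screening diagnosis. Much of this stands, and it is probably what the authors intended. But the baseline exception is written out, in 3.3.4 and 4.5.2, and this one is not. The rule is stated for efficacy analyses, and a primary endpoint should not depend on inferred precedence.

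On timing, the defence is that 3.3.2's rule is explicit and declines to separate failure from new infection, so only its rationale is inaccurate. That also stands. BV that is still present at Visit 2 counts either way. Only early positives that clear and do not return are affected.

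A reader might go further and treat every first positive found at an unscheduled visit as at risk. The documents do not support that. Positives outside a window are untouched by 4.5, those at 22 days or later are untouched by the timing point, and women who are positive again remain recurrent. Nor do they support the view that 4.5 undermines the adverse event summaries: SAP 9.3 includes all reported events, and 9.3.1 specifies maximum severity over 24 weeks.

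**Conclusion.** SAP 4.5 is wrong as written, with a small effect. Taken literally, it gives a value of the primary endpoint that contradicts 3.3.2, 8.1 and 8.2. This happens only for a woman with two evaluable results in one window, no other positive through the visit of interest, and no treatment or discontinuation that triggers 6.3.2. The premise in 3.3.2 is also inaccurate for unscheduled or early-termination visits before about study Day 15-18.

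The number of women affected cannot be derived from the documents and is probably very small. The power figures above show only what assumed rates would do. They rest on the design assumptions of SAP 5 and on equal rates in both arms. It would be too strong to infer that the primary result is unreliable, or that the endpoint must be redefined with a hard 22-day floor: the any-positive rule is explicit, and every in-window scheduled visit satisfies the premise.

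**What to change.** Before unblinding:

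1. In SAP 4.5, state that the closest-value and tie rules apply only to by-visit summaries. Cumulative and time-to-event recurrence use any positive diagnosis at any scheduled or unscheduled visit after enrollment, as in 3.3.2.
2. In SAP 3.3.2, correct the premise: in-window scheduled visits fall at least 22 days after MetroGel start, but unscheduled and early-termination visits may not. Keep the primary definition.
3. Add a sensitivity analysis of the primary endpoint that does not count a positive less than 22 days after MetroGel start unless BV is also present at a later visit. State how a woman with no later evaluable visit is handled, and that recurrences assigned under 6.3.2 are unaffected.

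The cost is a few sentences and one additional table. No new data are needed, since dates and results are already collected and listed.

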4.5.1. Safety Variables

Solicited local and systemic events are captured on a memory aid starting on Day 1, the first day of dosing daily through Week 1 and then weekly, continuing through Visit 7 (Week 24, Day 168). The subject is to record the presence and intensity of solicited events on the memory aid. Any event that is present at the time that the subject is screened should be considered as baseline and not reported as a solicited urogenital AE. However, if the symptom deteriorates at any time during the study, it is recorded as an AE. If a symptom is reported that is not present at baseline, it too is recorded as an AE. Solicited local events include vaginal bleeding other than menstruation, abnormal vaginal discharge, abnormal vaginal odor, genital itching, genital

burning, external genital irritation, external genital swelling, and genital rash. Solicited systemic events include nausea, vomiting, abdominal pain/cramps, diarrhea, constipation, pain/burning with urination, frequent urination, blood in urine, and headache.

Severity of solicited events symptoms are graded according to the tables in Appendix B and Appendix C in the protocol. Symptoms not specifically mentioned will be graded using the following scale:

- Mild: Events require minimal or no treatment and do not interfere with the subject's daily activities.
- Moderate: Events result in a low level of inconvenience or concern with the therapeutic measures. Moderate events may cause some interference with functioning.
- Severe: Events interrupt a subject's usual daily activity and may require systemic drug therapy or other treatment. Severe events are usually incapacitating.

Tolerability of LACTIN-V will be measured by identifying subjects who discontinue study product early due to adverse events.

4.5.2. Efficacy Variables

See Section 3.3 for efficacy variable definitions. BV recurrence is the primary efficacy variable. Amsel criteria and Nugent scores will be determined at each follow-up visit to diagnose BV according to the definition in Section 3.3.1. BV diagnosis at the screening visit will be used as the baseline BV diagnosis (see Section 3.3.2). Vaginal specimens will be analyzed for vaginal colonization with *L. crispatus* using qPCR assays and will be performed by a central laboratory. Concentrations of *L. crispatus* will be collected and used to determine the presence or absence of colonization. Acceptability of LACTIN-V will be measured by treatment compliance and responses to the self-administered questionnaire.

5. SAMPLE SIZE CONSIDERATIONS

Sample size calculations are based on the assumption of detecting a 50% reduction in the cumulative proportion of subjects who experience BV recurrence by 12 weeks post-administration of study product among subjects receiving LACTIN-V compared to those receiving placebo in a complete case analysis at the 0.05 significance level. The proportion of subjects among controls who will experience BV recurrence at 12 weeks is assumed to be 30%. We assume a LACTIN-V to placebo allocation ratio of 2:1 and 10% of subjects drop-out from the Complete Case population. Given logistical and feasibility constraints on the sample size and that this is a Phase II-b trial, which will provide screening evidence about safety and efficacy for a subsequent Phase III trial, this trial is powered at the 70% level. Given the assumptions above, a sample size of 228 subjects is required to detect a 50% reduction in the cumulative proportion of subjects experiencing recurrence in the Complete Case population with 70% power using the Pearson Chi-Square test.

6. GENERAL STATISTICAL CONSIDERATIONS

6.1. General Principles

Tabulations will be used extensively to summarize the data. All continuous variables will be summarized using the following descriptive statistics: n (sample size), mean, standard deviation, median, maximum, and minimum. The frequency and percentages (based on the sample size) of observed levels will be reported for all categorical measures. Wilson confidence intervals for binomial proportions and differences in binomial proportions will be computed for efficacy variables. Blaker confidence intervals for binomial proportions and differences in binomial proportions will be computed for safety variables. For the hypothesis tests comparing treatment groups with respect to safety outcomes, the two-sided Fisher's Exact test will be used. For the hypothesis tests comparing treatment groups with respect to efficacy outcomes, the two-sided Chi-Square test will be used. For all tests, a 5% two-sided significance level will be used.

For all efficacy outcome measures, the Complete Case population (see Section 6.3) will be used as the primary analysis population and the Per Protocol, modified Intent-to-Treat, and Intent-to-Treat populations will be used as secondary analysis populations. For all safety analyses, the Safety population will be used as the analysis population.

All summary tables will be structured with a column/sub-table for each treatment group (LACTIN-V, Placebo, and All Subjects). In general, all data will be listed by treatment group and/or subject, and when appropriate by visit number within subject. The total population size relevant to that table/column if applicable, including any missing observations will be displayed in the tables.

Note that in the data listings, Subject ID is the unique subject identifier, not the Study ID used on study and dates will not be included, only Study Day. Study Day 1 will be the day of the first dose of treatment.

6.1.1. Pseudo Code

The following SAS® pseudo code will be used to calculate the following:

Chi-Square test at 5% two-sided significance level and odds ratio (and 95% asymptotic CI) from 2x2 table:

```
proc freq;
  Table treatment*analysis_variable / chisq;
  ods output ChiSq=outputdsn1;
  ods output RelativeRisks=outputdsn2;
run;
```

Fisher's Exact test at 5% two-sided significance level:

```
proc freq;
  Table treatment*analysis_variable / exact;
  ods output FishersExact=outputdsn;
run;
```

95% Wilson CI for proportions/percentages:

```
proc freq;
  Table treatment*analysisvariable / binomial(wilson);
  ods output binomialcls=outputdsn;
run;
```

95% Wilson CI for difference in proportions (produces Newcombe CI):

```
proc freq;  
  Table treatment*analysisvariable / riskdiff(cl=Wilson);  
  Exact Riskdiff;  
  ods output pdiffcls=outputdsn;  
run;
```

95% Exact Blaker CI for proportions/percentages:

```
proc freq;  
  Table treatment*analysisvariable / binomial(blaker);  
  ods output binomialcls=outputdsn;  
run;
```

Time to event analysis to estimate number of events, median (and other quartiles) time to event, and Kaplan-Meier curves:

```
ods output CensoredSummary =_censorsum Quartiles =_quartiles;  
proc lifetest plots=survival;  
  time studyday*eventstatus(0);  
  strata treatment;  
run;
```

Poisson regression analysis to estimate event rate in each treatment group and rate ratio between treatment groups (with associated 95% CIs):

```
proc genmod;  
  class treatment;  
  model eventcount = treatment / dist=poisson link=log offset=logfollowuptime;  
  lsmeans treatment / ilink diff cl;  
run;
```

Repeated measures logistic regression analysis using Generalized Estimating Equations to estimate odds of event in each treatment group and odds ratio between treatment groups (with associated 95% CIs):

```
proc genmod;  
  class subjectid treatment other_covariates / param=glm;  
  model outcome=treatment other_covariates / dist=bin;  
  repeated subject=subjectid / type=ind/un/exch/ar(1);  
  lsmeans treatment / ilink exp diff cl;  
run;
```

Smoothing spline regression with different curves for each treatment group (with 95% confidence bands):

```
proc transreg;  
  model identity(outcome) = class(treatment / zero=none) | spline(day / knots=0 to  
  max_day by 1);  
run;
```

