3.3.3. Successful Colonization of *L. crispatus*

Colonization of *L. crispatus* will be determined from the concentrations of *L. crispatus* species and *L. crispatus* CTV-05 obtained from qPCR. Successful colonization is defined as follows:

- If CTV-05 concentration is above the lower limit of detection (LLOD) and the *L. crispatus* is above the LLOD, then successful colonization has occurred.
- If either CTV-05 or *L. crispatus* concentration is below LLOD or indeterminate, then successful colonization has not occurred.

The LLOD for CTV-05 is 660 copies/mL and the LLOD for *L. crispatus* is 953 copies/mL.

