Table 35, Table 36, Table 37, and Table 38 will present *L. crispatus* colonization by study day, treatment group, and number of partners for each analysis population. Number of partners will be categorized as “No partners,” “1 Partner,” and “>1 Partner” from data obtained from the sexual history interview. Depending on the distribution of number of partners, other cutpoints may be examined. Figure 14, Figure 15, Figure 16, and Figure 17 will present *L. crispatus* CTV-05 concentration by study visit, treatment group, number of partners, and analysis population.

Summaries of days since last dose (mean, median, standard deviation, range) will be presented by *L. crispatus* colonization status will be presented in Table 39, Table 40, Table 41, and Table 42. *L. crispatus* CTV-05 concentration and time since last dose will be presented graphically for each visit, treatment group, and analysis population in Figure 6, Figure 7, Figure 8, and Figure 9. A smoothing spline regression model will be fit with treatment group as an independent variable. The fitted curves with 95% confidence bands will be included in the figures. Model fit and inference of the parameters will be commented on in the final report but not included in a table.

L. crispatus colonization will be presented by treatment compliance status in Table 43, Table 44, and Table 45. Treatment compliance will be categorized as “Compliant” or “Not compliant,” and will be assessed from the start of treatment administration up until the visit listed. See Section 9.2 for measurements of

treatment compliance. Box plots of *L. crispatus* CTV-05 concentration by treatment compliance status are provided for each treatment group, visit, and analysis population in [Figure 18](#), [Figure 19](#), and [Figure 20](#).

Summaries of days since the last day of the last menstrual period (mean, median, standard deviation, range) by *L. crispatus* colonization status will be presented in [Table 46](#), [Table 47](#), [Table 48](#), and [Table 49](#).

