Occurrence of menses will be captured on the memory aid. *L. crispatus* CTV-05 concentration and time since last day of the last menstrual period will be presented graphically for each visit, treatment group, and analysis population in [Figure 21](#), [Figure 22](#), [Figure 23](#), and [Figure 24](#). A smoothing spline regression model will be fit with treatment group as an independent variable. The fitted curves with 95% confidence bands will be included in the figures. Model fit and inference of the parameters will be commented on in the final report but not included in a table.

L. crispatus colonization will be also be presented by occurrence of menses after the last dose taken in [Table 50](#), [Table 51](#), [Table 52](#), and [Table 53](#). Subjects will be categorized as menstruating after their last dose taken before the visit presented, or not menstruating after the last dose taken before the specified visit. If there are less than three subjects in either treatment group who had menses since their last dose for a specified visit, that visit will be excluded from the table. Box plots of *L. crispatus* CTV-05 concentration by occurrence of menses are provided for each treatment group, visit, and analysis population in [Figure 25](#), [Figure 26](#), [Figure 27](#), and [Figure 28](#).

For all by-visit summaries, the proportions of subjects with colonization at a visit is defined as follows: the numerator is the number of subjects who experience recurrence at the specified visit and the denominator of the proportion of subjects with BV recurrence is the number of subjects in the analysis population and subgroup who returned for that visit.

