xx	xx	xxxxxxx	xxxxxxxxxxx	xxxxxxx	Yes/No	Yes/No	Yes/No	Yes/No	xxxxxxxxxxx
xx	xx	xxxxxxx	xxxxxxxxxxx	xxxxxxx	Yes/No	Yes/No	Yes/No	Yes/No	--

Note: Deviation description column will contain all subfields concatenated together

Implementation Notes:

1. Sort order will be by Actual Treatment Group, Subject ID, Deviation Number
2. In the Deviation Category column concatenate any specify fields
3. In the Reason for Deviation column concatenate any specify fields.

Listing 5 Non-Subject-Specific Protocol Deviations

Site	Deviation	Start Day	End Day	Reason for Deviation	Deviation Resulted in Subject Termination?	Deviation Affected Product Stability?	Deviation Category	Deviation Resolution	Comments
xxxx	xxxx	xx	xx	xxxx	Yes/No	Yes/No/NA	xxxx	xxxx	xxxx
xxxx	xxxx	xx	xx	xxxx	Yes/No	Yes/No/NA	xxxx	xxxx	xxxx

Note: Deviation column will contain all subfields concatenated together

Implementation Notes:

1. Sort order will be by Site Name, Start Date
2. In the Deviation Category column concatenate any specify fields
3. In the Reason for Deviation column concatenate any specify fields.

Listing 6 Individual Efficacy Response Data

Study Day (Week)	Homogeneous, thin, grayish-white discharge	Vaginal pH	Amine (“whiff”) test on KOH wet mount	Clue Cells on wet mount (%)	Amsel Criteria	Nugent Score	BV Diagnosis	L. crispatus Concentration (copies/mL)	CTV-05 Concentration (copies/mL)	Lactobacillus spp. Concentration (copies/mL)	Total Bacteria Concentration (copies/mL)	L. crispatus Colonization Status
Actual Treatment Group: , Randomized Treatment Group: Subject ID:												
x (x)	Present/ Absent/ Not Assessed	xx.x	Negative/ Positive/ Not Assessed	xx	x	x	Positive/ Negative/ Indeterminate	x.x E x	x.x E x	x.x E x	x.x E x	Successful/ No colonization

Implementation Notes:

1. Sort order is actual treatment group, Subject ID, Study Day.
2. If all subjects received the correct treatment, only display “Treatment Group”.

Listing 7 Compliance Data- All Treated Subjects

Actual Treatment Group	Subject ID	Week	Dose	Dose Taken? (Subject Report)	Study Day of Administration (Subject Report)	Time of Administration (Subject Report)	Number of Applicators Returned (Used / Unused)	Staining Assessment (Used / Unused / Indeterminate)	Compliance Status
xxxxxx	xxxxxx	1	1	Yes/No	xx	xx:xx	x / x	x / x / x	Compliant/Non-compliant
			2	Yes/No	xx	xx:xx			
			3	Yes/No	xx	xx:xx			
			4	Yes/No	xx	xx:xx			
			5	Yes/No	xx	xx:xx			
		2	1	Yes/No	xx	xx:xx	x / x	x / x / x	

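### The SAP's smoothing-spline code puts an unpenalised knot at every day, so on whole-day data it smooths nothing and leaves its coefficients unidentified

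*SAP*

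**What the plan says.** SAP 6.1.1 introduces the block as "Smoothing spline regression with different curves for each treatment group (with 95% confidence bands" and gives the model as "model identity(outcome) = class(treatment / zero=none) | spline(day / knots=0 to" the maximum day, in steps of one day. No penalty, smoothing parameter or selection criterion appears.

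SAP 8.2 uses it twice. Against time since dose (Figures 6–9), "CTV-05 concentration and time since last dose will be presented graphically for each visit, treatment group, and analysis population". Against menses (Figures 21–24), "CTV-05 concentration and time since last day of the last menstrual period will be presented graphically for each visit, treatment group, and analysis population". For both, "A smoothing spline regression model will be fit with treatment group as an independent variable", the figures carry 95% bands, and "Model fit and inference of the parameters will be commented on in the final report but not included in a table".

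On units, SAP 3.3.3 says "The LLOD for CTV-05 is 660 copies/mL", and Listing 6 also shows the concentration in copies/mL. The visible text states neither the scale on which concentration is modelled nor a numeric value for results below the limit of detection (LLOD).

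**The concern.** A smoothing spline trades fit against roughness, so the curve shows a trend rather than the scatter of individual days. A knot at each day with no penalty removes that trade-off. The curve then follows day-to-day noise, and its coefficients have no unique values to report on. The menses figures bear on secondary objective 1 (colonization in relation to menses). A reader could take a jagged line for a cyclical pattern, or miss a real change inside a needlessly wide band.

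**Working it through.** **1. Women available per visit.** SAP 5 gives 30% versus 15% recurrence, two-sided 5%, 70% power, 2:1 allocation and 10% dropout. With pooled proportion (0.30 + 2×0.15)/3 = 0.20:

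n(placebo) = [1.960·√(1.5×0.20×0.80) + 0.524·√(0.30×0.70 + 0.15×0.85/2)]² / 0.15² = (0.960 + 0.274)² / 0.0225 ≈ 67.7, so 68.

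The total is 3×68 = 204, and 204/0.9 = 226.7, so 227. The stated 228 is the next multiple of three, so the plan's figure is reproduced. It gives 152:76 randomized, or about 137:68 after 10% dropout.

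**2. Columns against information.** Assume a cubic spline (the code states no degree) and whole days 0 to M.
- Nominal columns per arm: 1 + 3 + (M + 1) = M + 5.
- Distinct days: M + 1, which is the largest rank possible.
- At M = 14 there are 19 columns and rank 15. At M = 25 there are 30 and rank 26. At M = 28 there are 33 and rank 29.
- At M = 25, leaving out the two end knots (which add nothing) still gives 28 columns for rank 26. The fitted values equal the day means to about 1e-15.

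The curve is therefore saturated. Fitted values are determined at the observed days. The separate coefficients are not determined, nor is the curve between observed days.

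**3. Data behind each point** (women spread evenly).
- M = 25: 137/26 = 5.3 LACTIN-V and 68/26 = 2.6 placebo women per day.
- M = 14: 9.1 and 4.5.
- M = 4: 27.4 and 13.6.

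**4. Cost in band width.** A fit with p coefficients from n women has typical fitted-value variance σ²p/n. A cubic with two knots has p = 6 per arm, so the expected width ratio is √((M + 1)/6): 1.6, 2.1 and 2.2 for M = 14, 25 and 28. Simulation (137:68, days uniform, log10 outcome with SD 1.5, LACTIN-V curve) gives slightly more, because women do not fall evenly across days:

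| M | Half-width, daily knots | Half-width, two knots | Ratio |
|---|---|---|---|
| 14 | 1.02 | 0.61 | 1.7 |
| 25 | 1.40 | 0.61 | 2.3 |
| 28 | 1.50 | 0.61 | 2.5 |

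At SD 1.0 the ratios are the same for M = 14 and M = 25 (0.68/0.41 and 0.94/0.41). Pointwise coverage was about 95% for both fits.

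**5. Where it bites.** SAP 4.4.3 sets dosing gaps of about 48 to 96 hours and no dose within 48 hours of a visit. Adherent women at Weeks 4 and 8 therefore span about days 2–4, and joining a few well-populated daily means does little harm. Days since menses range over a whole cycle, with a longer tail because women amenorrheic on contraceptives are eligible. Time since dose also spreads out at Weeks 12 and 24.

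**6. Scale, conditional.** If raw copies/mL were modelled, simulated coverage with daily knots was 77–93% at log10 SD 1.0, 51–67% at 1.5 and 18–28% at 2.0. Fewer knots alone would not repair this: with two knots on raw copies, coverage was 19–78% over the same SDs. No SD or day distribution is given in the documents, so these are assumed ranges.

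**The case against.** **A reader might infer that raw copies are modelled.** The documents do not establish this. `identity(outcome)` applies no further transformation to a placeholder variable, and a log10 variable derived beforehand fits the same line. Listing 6 uses scientific notation for copies/mL while Tables 27–30 use plain two-decimal placeholders, which does not favour the raw reading. The figure mock-ups, whose axes might settle it, are not visible and cannot count against the plan. What stands is that the visible text does not state the scale or the below-LLOD value.

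**A reader might infer that the daily knots make the 95% bands invalid.** They do not. On log10 they cover at about the nominal level at observed days; the cost is width and jaggedness. Under-coverage depends on the raw scale, which is not shown.

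**The figures are supplementary.** This stands. The secondary outcome is the proportion colonized, which is tabulated without the spline, and menses is also shown by tables and box plots. The code has open placeholders, and the SAP says model fit will be commented on. That limits the consequence, but the knot sequence is written out explicitly and contradicts its label.

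**The replacement is not exact either.** This also stands. A two-knot log10 fit with one shared residual variance was simulated with below-LLOD values set to LLOD/2. It assumed 50–78% colonized on LACTIN-V and 0–3% on placebo, mean log10 6.5 and SD 1.0–1.5. Coverage was 89–90% for LACTIN-V and about 100% for placebo.

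**Conclusion.** Wrong as written, with small consequences. The mismatch between label and code is certain from the text. Exact saturation needs days recorded as whole numbers; with hours or fractional days the fit is heavily over-parameterised instead. The 1.7- to 2.5-fold widening assumes days uniform over 0–14 to 0–28 and log10 SD 1.0–1.5. Comment on individual coefficients would have no basis, and no table would let a reader check it. The harm falls mainly on Figures 21–24 and on later visits. The primary analysis and the sample size are unaffected.

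**What to change.** In SAP 6.1.1, replace the daily knot sequence with a penalised spline (for example PBSPLINE) or two to three pre-specified knots. In SAP 8.2:
- state that the outcome is log10 concentration, with a stated value for results below the LLOD;
- confine comment to the fitted curves rather than individual coefficients;
- note that many below-LLOD values, especially on placebo (which contains no CTV-05), make the bands approximate.

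Both the knot change and the scale statement are needed. The cost is one line of code and a few sentences, with no new data and no effect on other analyses.
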